3.0	
Minimal changes were made to reflect the updated version of CIP	[name], Sr. Principal Biostatistician

2 List of Abbreviations and Definitions of Terms

Term	Definition/Acronyms
ADE	Adverse Device Effect
AE	Adverse Event
ASA	American Society of Anesthesiology
BIS™	Bispectral Index (BIS) technology monitoring uses processed EEG signals to measure sedation depth based on the level of consciousness
CBC	Complete Blood Count
CO ₂	Carbon Dioxide. It can be measured with a capnograph, a device that measures the concentration of carbon dioxide from each inspired and expired breath. Gases are collected with a non-invasive side stream from the inhaled and exhaled gases of the subject. Capnograph outputs numeric values and waveforms of the fractionated concentration of CO ₂ of each breath
CRF	Case Report Form. Forms where the clinical data are collected. eCRF is the electronic version of the CRF
EC	Ethics Committee
ECG	Electrocardiogram. A diagnostic tool that measures and records the electrical activity of the heart
ED	Effective dose
EDC	Electronic Data Capture. Electronic systems where the data are collected through the eCRF (Oracle Clinical). May also be referred to as RDC (Remote Data Capture).
EEG	Electroencephalogram
ET	End-tidal concentration

[BIS] Statistical Analysis Plan

Revision [\[x\]](#)

Page 4 of 20

Form

Medtronic

Term	Definition/Acronyms
EMR	Electronic Medical Record. Digital version of a patient's medical record within a single facility.
EtCO ₂	End-tidal Carbon Dioxide. The value of exhaled carbon dioxide displayed by the capnograph device
GCP	Good Clinical Practice
ICF	Informed Consent Form
IRB	Institutional Review Board
ISF	Investigator Site File. Regulatory binder supplied by the sponsor
LMA	Laryngeal mask
LOC	Level of consciousness
MAC	Minimum alveolar concentration
MOAA/S	Modified Observer's Assessment of Alertness/Sedation
PI	Principal Investigator. The person responsible for overseeing the study and assuring study completion in compliance with applicable regulations.
PIC	Patient Interface Cable
PK/PD	Pharmacokinetics and pharmacodynamics
SpO ₂	A non-invasive spectroscopic estimate of arterial oxygen saturation measured transcutaneously by a pulse oximeter
SAP	Statistical Analysis Plan
SOP	Standard Operating Procedures
TCI	Target-controlled infusion
TIVA	Total Intravenous Anesthesia
UADE	Unanticipated Adverse Device Effect

3 Introduction

The Evaluation of BIS™ and Levels of Sedation in Health Volunteers (OLIVER) Study is a multi-center, prospective randomized study to collect data to evaluate the relationship between BIS™ and inhaled anesthetics without and with opioids. Healthy Volunteers will be sequentially assigned to one of the study groups of anesthetics regimens at each clinical site. The BIS™ bilateral sensor will be placed on the subject's forehead to study the effects of these drugs on the brain. Each volunteer will be given a dose range of sequences of the target drug to achieve targeted drug concentration. Five groups of anesthetics regimens will be studied as follows:

1. Sevoflurane alone
2. Sevoflurane with Remifentanil
3. Sevoflurane with Fentanyl
4. Desflurane alone
5. Isoflurane alone

At each steady-state step, and after at least 12 minutes to achieve equilibrium, the Modified Observer's Assessment of Alertness/Sedation (MOAA/S) scale will be used to perform sedation/loss of consciousness assessment. The loss of verbal response will be defined according to the MOAA/S score value < 2 (0-1) and the presence of verbal response at values ≥ 2 (2-5).

The expected duration of each subject's participation is approximately 6 hours for both enrollment and procedure. The Enrollment Visit should take approximately 2 hours to complete, and the Study Visit will be approximately 4 hours per subject. Each subject will be contacted by phone within 48 hours of the study participation. Subjects will be continuously monitored throughout the study.

This document provides a detailed description of the statistical methods and procedures to be implemented during the analysis of the study.

This statistical analysis plan (SAP) is based on Version 5.0 of the Protocol dated on 06-JAN-2022.

4 Study Objectives

4.1 Primary Objective:

To determine BIS₅₀ (BIS™ value at which 50% of subjects will be unresponsive at a given drug concentration).

4.2 Secondary Objective:

To determine BIS₉₅ (BIS™ value at which 95% of subjects will be unresponsive at a given drug concentration).

[BIS] Statistical Analysis Plan

Revision [\[x\]](#)

Page 6 of 20

Form

Medtronic

To determine Prediction Probability score (P_k) for correctly predicting if the subject was responsive or unresponsive.

5 Investigation Plan

This is a multi-center, prospective randomized, two-stage design study to collect data to evaluate the relationship between BIS™ and inhaled anesthetics with opioids. Subjects will be enrolled in the study once all eligibility requirements for the study have been met. Subjects who give informed consent for the protocol in order to undergo screening for eligibility are not considered enrolled and should not be enrolled until the screening is completed. All subjects are healthy volunteers.

After the subjects are enrolled, they will be sequentially assigned to one of the study groups of anesthetics regimens at each clinical site. The BIS™ bilateral sensor will be placed on the subject's forehead to study the effects of these drugs on the brain. Each volunteer will be given a dose range of sequences of the target drug to achieve targeted drug concentration. Five groups of anesthetics regimens will be studied as follows:

- Sevoflurane alone
- Sevoflurane with Remifentanil
- Sevoflurane with Fentanyl
- Desflurane alone
- Isoflurane alone

At each steady-state step, and after at least 12 minutes to achieve equilibrium, the Modified Observer's Assessment of Alertness/Sedation (MOAA/S) scale will be used to perform sedation/loss of consciousness assessment. An anesthesiologist authorized to administer sedation drugs will be responsible for administering any procedural drugs for the sedation and monitoring of subject safety and physical state. All other personnel involved with the safety monitoring of subjects must be trained in and familiar with the management of recovery of sedated patients. The study site should have a setting that is fully equipped for the monitoring and support of the respiratory and cardiovascular function. Subjects will be continuously monitored throughout the study.

A two-stage design is used in this study. For each regimen group, 10 subjects will be enrolled in stage 1, and upon evaluation, up to 20 additional subjects will be enrolled in stage 2. With 5 regimen groups, a maximum of 150 subjects will be enrolled. An interim review will take place at the end of stage 1 (50 subjects, 10 subjects per regimen group). Both the primary and secondary objectives will be evaluated during the interim review, and one or more groups may be dropped upon interim results for safety concern (unacceptable safety events per clinical judgment).

Based on the number of sites and enrollment rates, study duration is expected to be up to approximately 9 months. The expected duration of each subject's participation is approximately 6 hours for both

[BIS] Statistical Analysis Plan

Revision [\[x\]](#)

Page 7 of 20

Form

Medtronic

enrollment and procedure. The Enrollment Visit should take approximately 2 hours to complete, and the Study Visit will be approximately 4 hours per subject. Each subject will be contacted by phone within 48 hours of the study participation. The Schedule of Events, **Table 1**, summarizes the intervals and data collection procedures.

Table 1: Schedule of Events

Study Tasks	Pre-screening No visit	Enrollment Visit 1	Execution Visit 2		Follow up Phone call
			Prior to Procedure	Procedure	
Eligibility Assessments					
Online or phone call pre-screening survey	x				
Informed Consent ¹		x			
Demographics		x			
Medical History		x			
Physical Exam		x			
Pulmonary function test		x			
Single 12-lead ECG		x			
Urine sample for the presence of cotinine		x	x		
Urine pregnancy test (Female)		x	x		
Complete blood count			x		
Inclusion/exclusion assessment		x	x		
Vital monitoring		x	x	x	
Concomitant Medication		x	x		
Urine drug screen and alcohol breathalyzer			x		
Safety Monitoring				x	
Sensors application				x	
The procedure with drug administration				x	
MOAA/S assessment				x	
Safety Assessments and Compensation					
Adverse Event Assessment ²		x	x	x	x
Device Deficiency ³				x	
Participant stipend ⁴		x		x	

Formatted: Not Highlight

6 Determination of Sample Size

A two-stage adaptive design is used in this study. For each regimen group, 10 subjects will be enrolled in stage 1, and upon evaluation, up to 20 additional subjects will be enrolled in stage 2. With 5 regimen groups, a maximum of 150 subjects will be expected.

[BIS] Statistical Analysis Plan

Revision [\[x\]](#)

Page 8 of 20

Form

Medtronic

Based on the dose-response relationship (logistic regression) with an allowable error of $\pm 15\%$ for BIS_{50} and coefficient of variation (CV) of 25% at the alpha level of 0.05, the sample size will provide sufficient power ($>80\%$) to evaluate the performance of anesthetic agents. An interim review will take place at the end of stage 1 (50 subjects, 10 subjects per regimen group).

In terms of hypothesis testing, let BIS_{50} be unit 1. With 25% coefficient of variation, the standard deviation (σ) is calculated as $BIS_{50} \times CV = 0.25$. To detect 15% difference (allowable error), the target hypothesis can be written as:

$$H_0: \mu = 1 \quad vs. \quad H_a: \mu = 1.15.$$

With two-sided alpha of 0.05 and power of 80%, the required sample size is 24 (PASS – Tests for One Mean). Of note that the statistical approach has been published in the literature (see reference: Kopman 2011).

By further considering the interim review and adaptiveness of design, we expect at least 80% data information will be retained from Stage 1, leading to a minimum *effective sample size* of $10*0.8+20 = 28$ for the final analysis. Adding 2 more subjects to have 30 subjects in each regimen will ensure adequate data to evaluate the dose-response relationship.

7 Statistical Methods

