7.3 Center Pooling

This is a multi-center clinical study, with standardization of subject enrollment, data entry and Adverse Event reporting. All investigational sites will follow the requirements of a common protocol, data collection procedures and forms. Upon justifications, data from all sites will be pooled for analysis.

Analyses to justify pooling will include the following:

Data Pooling Across Sites

Poolability across sites will be assessed using logistic regression model on the primary outcome. The model will include “Responsive: Yes/No” as response variable, and BIS, Site, BIS*Site interaction as exploratory variables. Sites with fewer than five subjects will be combined based on the order from smallest to largest. A P-value of 0.15 or less is considered statistically significant for the evaluation (FDA preferred).

If the sites are found to be significantly heterogeneous with respect to the primary outcome, additional analyses will be conducted to assess differences between sites in baseline and procedural variables that might explain differences in the primary outcome.

Data Pooling of Stage 1 and Stage 2

The study consists of two stages: first 10 subjects (stage 1), and then followed by 20 additional subjects (stage 2). Although no differences will be expected across the two stages, statistical testing will be performed to ensure the 2-stage data can be pooled for analysis. The testing will be based on the logistic regression model with binary “Responsive: Yes/No” as response variable, BIS, Stage indicator (X), BIS*X interaction as exploratory variables.

In case significant differences are present across the two stages, simply pooling data may not be valid. In this case, an alternative strategy will be used for statistical evaluation. Stage 1 data will be utilized as prior, which will be integrated into stage 2 data using the Bayesian Data Integration. More specifically, power prior and discounting function will be used to accommodate the difference across the two stages. Technical details can be found in the Appendix.

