$$P = \frac{e^{a+bX}}{1 + e^{a+bX}}$$

where P is the probability of “unresponsive”, X is the explanatory variable (BIS™ value or anesthetic agent concentration on the log scale), and a & b are corresponding model parameters.

In the context of the dose-response model, let θ represents the target BIS™ value on the log scale. Let $D = \{y_1\}$ and $D_0 = \{y_0\}$ represent the current data and prior data respectively. The parameter estimation will be carried out based on the posterior distribution (upon normalization):

$$\pi(\theta|D, D_0, \widehat{\alpha}_0) \propto L(\theta|D) L(\theta|D_0)^{\widehat{\alpha}_0} \pi_0(\theta)$$

where the notation $\widehat{\alpha}_0$ is used to denote that the estimate of α_0 based on the observed data. Of note that the estimate depends on the current data (D) and prior data (D_0). In conjunction with a pre-specified decision rule controlling the prior data weight, the estimate of $\widehat{\alpha}_0$ represents a measure of similarity between the current data and prior data. Alternatively, in the absence of $\widehat{\alpha}_0$, i.e., full weight would be given to the prior data.

C. Statistical Analysis

The Bayesian power prior with discounting function will be used to estimate the target parameter and determine $\widehat{\alpha}_0$, the strength of the prior data used to support the current data. Of note $\widehat{\alpha}_0$ ranges from 0 to 1, where 1 means that 100% of the prior data is used and 0 means that no prior data is used. Before beginning the current study, an initial value is chosen for $\widehat{\alpha}_0$, and let's call this value α_{max} . This α_{max} value is the maximum strength that the prior data can receive. For this study, we intend to use the same protocol and enrollment criteria for the prior and current studies, and therefore believe that a value of $\alpha_{max} = 1$ is appropriate.

The study data will be analyzed using the power prior method along with discounting function. The method will discount α_{max} to an appropriate value $\widehat{\alpha}_0$ where $\widehat{\alpha}_0 \leq \alpha_{max}$. This discounting scale is based on the discounting function which will be discussed in detail in the next section.

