Under the adaptive procedure, if the current study data diverges from the prior data, the discounting function will discount the strength of the prior data. Alternatively, if the prior and current study data agree, there will be no or minimal penalty from the discounting function, thus a large amount of data information would be integrated into current data for statistical inferences.

The primary analysis set consists of all evaluable subjects and will be used for the primary analysis. The per-protocol set will be used for supportive analysis.

D. Discounting Function Estimation Method

The method of power prior discounting function is comprised of four steps: **Compare, Discount, Combine, and Estimate**. Details in each step are presented below.

Compare:

We start by stochastically comparing current data vs prior data as follows.

For each study group, we separately fit the model to the combined prior and current data:

$$H(p_i) = \beta_0 + \beta_1 I(i \in \text{prior}) + \beta_2 d_i + \varepsilon_i, \quad \varepsilon_i \sim N(0, \sigma^2),$$

where H is the inverse logit function, p_i is the probability of target response, d_i is the dose concentration (log scale), and the indication function $I(i \in \text{prior}) = 1$ if the subject is from the prior data, and 0 otherwise. With a flat prior on each parameter, we estimate the posterior probability that $\beta_1 > 0$ by first computing the parameter, using Monte Carlo sampling

$$p^* = P[\beta_1 > 0 \mid D, D_0].$$

Having calculated the parameter for each group, we use the transformation:

$$p = \begin{cases} 2p^*, & p^* \leq 0.5 \\ 2(1 - p^*), & p^* > 0.5 \end{cases}$$

Now, under this transformation, if p is close to 0, there is a high probability that the current data and prior data come from different populations and discounting should be applied to reduce the influence of the prior. On the other hand, if p is close to 1, there is a high probability that the current data and prior data are from similar populations and minimal discounting should be applied.

Discount:

[figure not shown]
Let discount α_{max} based on the value of p from the **Compare** step and the discounting function $F(p)$,

$$\widehat{\alpha_0} = \alpha_{max} F(p),$$

where $F(p)$ is a function between 0 and 1. A two-sided Weibull function will be utilized as follows:

$$F(p) = 1 - e^{-(p/\lambda)^k}.$$

For this study, we will be using a shape parameter of $k = 3$ and a scale parameter of $\lambda = 0.5$ (illustrated below).

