table summarizes the assumptions that were made for the primary endpoint simulations, and the figure summarizes the operating characteristics for the discounting parameter.

Table: Simulation Assumptions for Primary Endpoint Analysis

Assumptions	Values
Prior Subjects	10
Current Subjects	20
BIS ₅₀ Value (Mean)	60
Prior Data BIS ₅₀ Value (CV%)	25%
Prior Data BIS ₅₀ Value (SD)	1.25
Current Data BIS ₅₀ Value (CV%)	25%
BIS ₅₀ Value Ratio (Current vs Prior)	1.15
Weibull Discounting Function Parameters	shape: $k = 3$, scale: $\lambda = 0.5$

Simulation results are summarized in the following figure. As expected, there is good distributional overlapping between the prior and current data. The amount of prior data integrated to the current data is quantified by the discounting parameter, which has a mean value of 90.4% with corresponding 95% credible interval (53.1%, 99.9%). Overall, the variations between prior and current data have been taken into account and valid statistical inferences can be made.

Figure: Posterior distribution of the discounting parameter (10k simulations)

G. References

- [1] <http://mdic.org/computer-modeling/virtual-patients/>

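### SAP section 6 treats 28 as the minimum effective sample size, but the discount rule has no floor (20 to 30), and Appendix I.F's 90.4% retention cannot be reproduced from that rule

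*SAP*

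**What the plan says.** SAP section 6 derives 24 subjects per regimen from a one-sample test of a mean: a 15% difference, CV 25%, two-sided alpha 0.05 and 80% power. It then allows for the two-stage design: "we expect at least 80% data information will be retained from Stage 1, leading to a minimum" effective sample size of 28. It concludes: "Adding 2 more subjects to have 30 subjects in each regimen will ensure adequate data".

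Appendix I.C sets the maximum Stage 1 weight at 1 and defines the scale as one "where 1 means that 100% of the prior data is used and 0 means that no prior data is used". Appendix I.D turns a similarity measure p into the weight F(p) = 1 − exp(−(p/λ)^k), with k = 3 and λ = 0.5. Appendix I.E includes a hypothetical panel in which the prior gets no weight. Appendix I.F reports 10,000 simulations with 10 prior and 20 current subjects, mean BIS50 of 60, CV 25%, prior SD 1.25 and a current-to-prior ratio of 1.15. They give mean retention of 90.4% with interval 53.1% to 99.9%.

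On when discounting applies, SAP 7.3 tests for a stage difference and, if it is significant, says: "In this case, an alternative strategy will be used for statistical evaluation". The power prior is that strategy. Appendix I.C states no such condition: "The study data will be analyzed using the power prior method along with discounting function". SAP 7.2.1 and Protocol 14.4 also describe the combination without it.

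**The concern.** A minimum has to be guaranteed by the rule that generates it, and nothing in Appendix I keeps the weight at or above 80%. Appendix I.F is the only quantitative support for the retention assumption. If its result does not follow from the stated rule, the SAP has no documented basis for expecting 80%.

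Two things are at stake. One is the power claim of more than 80%, which fails if less than about 40% of Stage 1 is retained. The other is the primary estimate, because BIS50 depends on whether Stage 1 is fully pooled or discounted, and the SAP can be read either way.

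**Working it through.** **The SAP's own figures.** For a one-sample two-sided t-test with effect 0.15/0.25 = 0.6 and alpha 0.05, the noncentral t gives n = 24 with power 80.4%, so 24 reproduces. The 28 is correct arithmetic if 80% is retained.

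**Range under the rule.** Effective n = 20 + 10 × weight, with weight from 0 to about 1. Half-width = t × 25%/√n.

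| Stage 1 weight | Effective n | Power | Half-width |
|---|---|---|---|
| 0 | 20 | 72.1% | ±11.7% |
| 40% | 24 | 80.4% | ±10.6% |
| 53.1% (Appendix I.F lower limit) | 25.3 | 82.6% | ±10.3% |
| 80% | 28 | 86.4% | ±9.7% |
| 100% | 30 | 88.8% | ±9.3% |

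**Appendix I.F against the rule.** Inverting F gives p = 0.5 × (−ln(1 − weight))^(1/3). A weight of 53.1% needs p = 0.456, 80% needs 0.586 and 90.4% needs 0.664. I read the reported interval as percentiles across the simulated trials. It then requires p ≥ 0.456 in 97.5% of trials.

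If the two stages are identical, p is approximately uniform on 0 to 1. Then:
- mean weight is 0.55, with 2.5% and 97.5% limits of 0.0001 and 0.999;
- the weight reaches 53.1% in 1 − 0.456 = 54% of trials and 80% in 1 − 0.586 = 41%;
- effective n is below 24 in 40% of trials.

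A true stage difference should lower these. At ratio 1.15 the SAP does not give the data-generating model, so I tried several:
- Two-sample approximation, CV about 25%, raw or log scale: mean weight 0.21 to 0.25.
- SD 1.25 on the raw scale in both stages: 0.00. With 1.25 for the prior and 15 for the current data: 0.04.
- SD 1.25 on the log scale in both stages: 0.54.
- Logistic Compare step (assumed log-threshold SD 0.246, slope 4 or 8, sevoflurane steps, 1.15 taken as a dose-threshold ratio): 0.30 to 0.36 with 7 to 8 observations per subject, and 0.42 to 0.46 with one. With identical stages this version gives 0.46 to 0.50.

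The lower 2.5% limit is about zero in all the two-sample runs. With one observation per subject, 6% to 41% of logistic fits did not converge and were dropped. Counting those as full weight raises the mean to 0.54 to 0.70, but the lower limit stays below 1%.

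**The SD entry.** 25% of 60 is 15. On the log scale, √ln(1 + 0.25²) = 0.246, and exp(0.246) = 1.28 as a geometric SD. The table's 1.25 equals neither, though it may be a rounded, unlabelled geometric SD.

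**If discounting follows only a significant stage test.** SAP 7.3 gives no threshold for this test; the site test there uses 0.15. I assumed 0.05 to 0.15 with identical stages, and fitted the stage test and the Compare step as separate models. Mean retention is about 95% to 87%. Effective n is below 28 in 5% to 15% of trials and below 24 in 5% to 12%. Below 24 means a weight under 40%, so the 2.5% limit is still under 53.1%.

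**Effect on BIS50.** A simple weighted mean at ratio 1.15 is (10w × 60 + 20 × 69)/(10w + 20): 66.0 at w = 1 and 69.0 at w = 0. If 60 is the Stage 2 mean, Stage 1 is 60/1.15 = 52.2, and the values are 57.4 and 60.0. The largest shift is 2.6 to 3.0 points.

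**The extra two subjects.** 10 × 0.8 + 20 already counts all 30 enrolled, so no two remain to add.

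**The case against.** Section 6 says the 80% is expected, so 28 can be read as a planning figure worded too strongly. That softens the 80%, but it does not make 28 a minimum.

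SAP 7.3 is explicit that the power prior follows a significant stage test, SAP 7.5 repeats that poolability will be tested, and Protocol 14.4 offers the Bayesian method only as an example and defers to the SAP. On this more natural reading, an expectation of at least 80% holds on average when the stages are alike. That stands. Appendix I.C nevertheless reads as unconditional, the threshold is missing, and values below 28 still occur.

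The simulation code and figure are not available, and some hybrids come close to the published result. Drawing data at CV 25% but scaling the comparison by a log SD of 1.25 gives 0.93 (0.63, 1.00). Using 1.25 for the prior only gives about 0.88 (0.43, 1.00). Neither matches, and both mix inconsistent SDs. They do suggest that the unexplained 1.25 may be the source of the discrepancy.

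Finally, the practical effect is small: the objective is estimation, p-values are for reference only, and no stage difference is expected. This also stands, and it limits the weight of the point.

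**Conclusion.** The concern holds. The 28 is an expectation conditional on 80% retention. The rule itself allows 20 to 30, with planning power from 72% to 89%. Appendix I.F's 90.4% (53.1%, 99.9%) is not reproducible from the stated rule and inputs. The identical-stages result needs only that p be roughly uniform and that discounting always apply. The figures at ratio 1.15 depend on assumed models and should be read as a range. What was actually simulated is unknown, so the finding is non-reproducibility, not a diagnosed error.

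The consequence is limited. Precision stays within ±15% even if Stage 1 is lost entirely, and power stays above 80% while at least about 40% of Stage 1 is kept. The unsettled combination rule matters more, because it could move BIS50 by up to 3 points if the stages truly differed by 15%.

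**What to change.** - In SAP section 6, replace the minimum of 28 with the range 20 (power 72%, ±11.7%) to 30 (power 89%, ±9.3%). Give 28 as the value if 80% is retained, and note that precision stays within ±15% throughout.
- Delete the sentence about adding two subjects.
- In Appendix I.F, correct the SD of 1.25 or label its scale, state the data-generating model, and re-run the simulation with p computed from each simulated trial by the Compare step.
- State whether the power prior applies always or only after a significant stage test, and give that test's threshold. Reconcile SAP 7.3 with SAP 7.2.1, Appendix I.C and Protocol 14.4.

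The cost is one simulation re-run and a few restated sentences. No subjects are added, and neither enrolment nor the estimand changes.
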